7.10.6.1 Efficacy Visit Windows

For the weeks on treatment (weeks prior to the follow-up period), the last day is always the last day of exposure to treatment.

The study week determination for the vasomotor symptoms data is based on the following:

Analysis study week	Actual assessment day
Baseline	7 non-missing days prior to D1
Week 1	D1 to D7
Week 2	D8 to D14
Week 3	D15 to D21
Week 4	D22 to D28
Week 5	D29 to D35
Week 6	D36 to D42
Week 7	D43 to D49
Week 8	D50 to D56
Week 9	D57 to D63
Week 10	D64 to D70
Week 11	D71 to D77
Week 12	D78 to D84 or last day of exposure to treatment, if this happened after day 84
Last on Treatment Week	Last 7 days of treatment
Follow-up Week 1	Day 1 FU – Day 7 FU ^
Follow-up Week 2	Day 8 FU – Day 14 FU ^
Follow-up Week 3	Day 15 FU – Day 21 FU ^

^ Day X FU is defined as last day of exposure to treatment + X

The assessment of a week will be derived if any information for 3 or more days was reported (morning dose, evening dose, or vasomotor symptom).

All other efficacy assessments, including those from unscheduled visits and regardless of visit label, will be allocated to analysis visits based on the table below:

CRF visit	Target day	Actual assessment day	Analysis visit
Visit 1	D-35	D-35 to D-1	Screening
Visit 2	D1	D1	Baseline
Visit 3	D29	D22 to D36	Week 4
Visit 4	D57	D50 to D64	Week 8
Visit 5	D85	D78 to Day 92	Week 12
End of treatment	Last dosing day	Closest observation to the date	EOT
Visit 6	D106	Last assessment after date of completion or termination of treatment period	Week 15 Follow-Up

The value which assessment day is the closest to the defined target day within these windows is used. If two values are equally close, the latter is used in the analysis.

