8.2 Pharmacokinetic Assessments

Venous blood samples will be collected for PK analysis of ESN364 and metabolite CCI in plasma according to the timepoints defined below and in the Schedule of Procedures. Subjects should be fasted (defined as nothing by mouth except water [up to 1 hour before study drug intake]) for at least 10 hours prior to study visit. During the postdose assessment period, the subject may eat and drink, provided this is done at least 1 hour after dosing.

Pharmacokinetic samples will be taken at Week 4 (Visit 3) predose and 1 (± 30 min), 3 (± 30 min), 5 (-1 h/+30 min), and 7 hours (-1 h/+2 h) postdose as well as predose at Week 12 (Visit 5). The indicated time windows for PK sampling will allow for flexibility. For the samples before the morning dose on Week 4 (Visit 3) and Week 12 (Visit 5) the time of the morning and evening dose of the previous day should be recorded. For the samples after the morning dose on Week 4 (Visit 3) the time of the morning dose should be recorded. If the subject is not fasted, PK assessments should still be completed and the time of last meal documented in the eCRF.

In the event that 1 or more PK samples are missed at Week 4 (Visit 3) or if the subject cannot accommodate this schedule, efforts should be made to collect PK samples for the missed timepoints at Week 8 [Visit 4] or Week 12 [Visit 5] or by means of an unscheduled visit. The time of dosing relative to these samples should be recorded as well. In the event that the subject cannot accommodate this schedule on Week 4 (Visit 3), this PK sampling may be shifted to a later visit.

The exact date and time of the PK sampling must be recorded in the source documents and on the eCRF as well as the exact time of last drug intake before the samples were taken. This means that for a predose blood sample, the time of the morning and evening drug intake of the day before needs to be recorded, and for the postdose samples, the exact time of the morning dose on the very same day needs to be recorded.

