8.3 Pharmacodynamic Assessments

Venous blood samples will be collected for PD assessments at Day 1 (Visit 2), Week 4 (Visit 3), Week 8 (Visit 4), Week 12 (Visit 5)/ET, and at the follow-up visit (Week 15 [Visit 6]). Subjects should be fasted (defined as nothing by mouth except water [up to 1 hour before study drug intake] for at least 10 hours prior to study visit. During the postdose assessment period, the subject may eat and drink, provided this is done at least 1 hour after dosing.

Samples will be taken predose at Day 1 (Visit 2), Week 8 (Visit 4), and Week 12 (Visit 5)/ET, as well as predose and 3 hours postdose at Week 4 (Visit 3). The Week 4 (Visit 3) 3-hour postdose PD sample should be shifted to a later date in cases where the subject cannot accommodate the PK sampling schedule at that visit. The PD sample should be taken at the same time as the 3-hour postdose PK sample (see Section 8.2). A PD sample will be taken at the follow-up visit (Week 15 [Visit 6]) as well. Markers include LH, FSH, E2, and SHBG.

The exact date and time of blood sampling must be recorded in the source documents and on the eCRF. Plasma will be collected and handled as specified in the central laboratory manual. After appropriate labeling, the plasma samples will be stored below -70°C at the study site. Thereafter, the frozen plasma samples will be transported/shipped on dry ice to the central laboratory for collection and storage below -70°C until analysis.

Further procedures for sample collection, shipment, processing, and storage are described in the laboratory manual.

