- g. Includes age, race, sex, and smoking status (smoker/non-smoker).
- h. Includes height (at the screening visit only), weight and waist circumference. A bimanual clinical pelvic and clinical breast examination will be performed at the screening visit. A bimanual clinical pelvic examination can be performed at any time in the study where clinically indicated.
- i. Weight and waist circumference only.
- j. Includes biochemistry, coagulation (at the screening visit and Week 12 [Visit 5]/ET only), and hematology panel. Blood samples for clinical laboratory tests should be taken in a fasted state (defined as nothing by mouth except water for 10 hours), except for Week 2 (Visit 2A), Week 6 (Visit 3A), and Week 10 (Visit 4A).
- k. Includes biochemistry and hematology, only.
- l. Includes oral/tympanic temperature, sitting blood pressure, and pulse rate (supine after 5 minutes of rest).
- m. All 12-lead ECGs will be captured in triplicate (ie, 3 separate 12-lead ECGs at least 1 to 2 minutes apart within a 5-minute window). The subject should rest in supine position for at least 10 minutes prior to the first ECG.
- n. Only in the event the subject does not have a normal/negative or no clinically significant findings Pap smear from previous 9 months on record.
- o. Subjects will undergo endometrial biopsy at Screening (if endometrial thickness is ≥ 4 mm), at Week 12 (end-of-treatment)-(all subjects), at the ET Visit for subjects who are withdrawn from the study prior to completion (if study drug exposure is ≥ 10 weeks), and in all cases of uterine bleeding. If the uterine biopsy is abnormal at Week 12 (end-of-treatment), subjects will have a repeat biopsy 4 weeks later, if clinically indicated.
- p. For HBsAG, anti-HCV antibodies, and anti-HIV antibodies.
- q. Samples will be taken predose at Day 1 (Visit 2), Week 8 (Visit 4), and Week 12 (Visit 5)/ET, as well as predose and 3 hours postdose at Week 4 (Visit 3). The Week 4 (Visit 3) 3 hours postdose PD sample should be shifted to a later date in cases where the subject cannot accommodate the PK sampling schedule at that visit. The PD sample should be taken at the same time as the 3-hour postdose PK sample (see Section 8.2). A PD sample will be taken at the follow-up visit (Week 15 [Visit 6]) as well. Markers include LH, FSH, E2, and SHBG.

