6.1.2 Secondary Efficacy Endpoints

The secondary efficacy endpoints include the effect of ESN364 on the following:

6.1.2.1 Vasomotor Symptom Endpoints:

- Mean change in the frequency of mild, moderate, and severe vasomotor symptoms from baseline to each study week;
- Mean change in the frequency of moderate and severe vasomotor symptoms per 24h from baseline to each study week;
- Mean change in the severity of mild, moderate, and severe vasomotor symptoms from baseline to each study week;
- Mean change in the severity of moderate and severe vasomotor symptoms from baseline to each study week;
- Mean change in the hot flash score of mild, moderate, and severe vasomotor symptoms from baseline to each study week;
- Mean change in the hot flash score of moderate and severe vasomotor symptoms from baseline to each study week;
- Mean percent reduction of mild, moderate, and severe vasomotor symptoms from baseline to each study week; and
- Mean percent reduction of moderate and severe vasomotor symptoms from baseline to each study week.

Frequency of mild, moderate and severe vasomotor symptoms is the number of mild, moderate and severe vasomotor symptoms per 24h (or 12h day time or 12h night time).

Severity of mild, moderate and severe vasomotor symptoms per 24h (or 12h day time or 12h night time):

$$\frac{[(\text{number of mild vasomotor symptoms} \times 1) + (\text{number of moderate vasomotor symptoms} \times 2) + (\text{number of severe vasomotor symptoms} \times 3)]}{\text{number of mild/moderate/severe vasomotor symptoms}}$$

Severity is zero for subjects who have no hot flashes.

Hot flash score per 24h (or 12 h day time or 12 h night time): The hot flash score per 24h (or 12 h day time or 12 h night time) of vasomotor symptoms (mild, moderate, and severe) is calculated as follows:

(number of mild vasomotor symptoms x 1) +
(number of moderate vasomotor symptoms x 2) +
(number of severe vasomotor symptoms x 3).

The hot flash score per 24h (or 12 h day time or 12 h night time) of moderate and severe vasomotor symptoms is calculated as follows:

(number of moderate vasomotor symptoms x 2) +
(number of severe vasomotor symptoms x 3).

A weekly frequency, severity, or hot flash score will be derived similar to the co-primary efficacy endpoints. See Section 7.10.6 for study week and endpoint derivations.

6.1.2.2 Responder Endpoints:

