6.1.2.4 Pharmacodynamics Markers

- Change from baseline to Week 12 in plasma concentrations of luteinizing hormone (LH), follicle-stimulating hormone (FSH), estradiol (E2), and sex hormone-binding globulin (SHBG).

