7.4.2 Analysis of Secondary Endpoints

The analysis of secondary efficacy endpoints will be based on the FAS.

For each of the secondary vasomotor symptom and patient-reported outcome endpoints, an MMRM model as described in Section 7.4.1.2 will be used. The treatment difference will be estimated at all study weeks (week replaced by visit for patient-reported outcome endpoints).

For each of the secondary responder endpoints, logistic regression will be used for the analysis for each week and endpoint. The analyses will include the treatment group and smoking status (current vs. former/never) as factors and baseline measurement (mean frequency of vasomotor symptoms) as a covariate. The missing value will be imputed as a non-responder.

[figure not shown]
For these responder endpoints, the number of subjects who achieve the reduction will be summarized by study week with descriptive statistics for each treatment arm. For 50% and 90% reduction responders, Kaplan-Meier estimate will be used to estimate the time to response and the time to sustained response. Smooth average (SA) will be used for the time to response. SA value for day X-1, day X and Day X+1 would be assigned to day X. The time to response will be the first day with at least 50% (or 90%) response for both original numbers and SA number. The time to sustained response will be the first day with at least 50% (or 90%) response for both original numbers and SA number, and SA response from that day till the end of the treatment at least 50% (or 90%) response on each day. For the non-responders, it will be censored at the end of treatment.

Diary interaction compliance will be summarized with descriptive statistics and presented by treatment group.

Plasma concentrations of hormones and bone turnover markers will be summarized with descriptive statistics for each treatment group at each visit. Additionally, a within-subject change will be calculated as the post-baseline measurement minus the baseline measurement and summarized in the same way. Pharmacodynamic data and efficacy data may be evaluated by a population PD or population PK/PD approach. All details of population analyses will be described in a separate analysis plan and a separate report will be written. When deemed necessary, data from this study may be combined with data from other studies.

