7.10.6 Visit Windows

The study protocol gives the overall study schedule for these visits expressed as the number of days relative to Visit 2. Study Day will be calculated as date of visit/assessment – first dose date +1. There will be no Day 0. Visit 2 is scheduled to be Day 1 if the patient takes the first dose on Visit 2, and the day immediately prior to Visit 2 is Day -1.

Subjects will not be excluded from analyses due to the subject's failure to comply with the visit schedule.

If baseline is missing, the screening assessment can be used.

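### Read literally, the SAP's tie rule makes the Week 4 hormone result a 3-hour postdose value, set against predose values at baseline, Week 8 and Week 12

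*SAP*

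**What the plan says.** Protocol 8.3 schedules one hormone sample per visit except at Week 4, where there are two: "as well as predose and 3 hours postdose at Week 4 (Visit 3". The footnote in SAP 2.2 gives the other on-treatment samples and baseline: "Samples will be taken predose at Day 1 (Visit 2), Week 8 (Visit 4), and Week 12 (Visit 5)/ET".

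SAP 6.1.2 opens with "The secondary efficacy endpoints include the effect of ESN364 on the following", and the hormones are one of its subsections (6.1.2.4). The endpoint there is "Change from baseline to Week 12 in plasma concentrations of luteinizing hormone (LH", with FSH, E2 and SHBG listed beside it. The table for non-diary efficacy data in SAP 7.10.6.1 therefore governs them. It assigns each value to an analysis visit by day, keeps the value nearest the target day, and breaks ties this way: "If two values are equally close, the latter is used in the analysis". SAP 7.10.6 defines the day: "Study Day will be calculated as date of visit/assessment – first dose date +1".

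On reporting, SAP 7.4.2 says: "Plasma concentrations of hormones and bone turnover markers will be summarized with descriptive statistics for each treatment group at each visit". Changes from baseline are summarized in the same way, and no time point is mentioned.

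Protocol 8.3 lets the 3-hour hormone sample move to a later date when the subject cannot fit the PK series at Week 4, and ties it to the 3-hour PK sample. For missed PK samples, protocol 8.2 says "efforts should be made to collect PK samples for the missed timepoints at Week 8 [Visit 4] or Week 12 [Visit 5", with an unscheduled visit as a further option.

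**The concern.** The tie rule appears to be written for two visits that fall equally far from target. Here it meets two planned samples on one day that differ by design in their timing relative to the dose. It resolves them in favour of the one that does not match baseline or the later visits.

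The effect of doses and regimens on PD markers is a secondary objective, and protocol 5.2 treats LH secretion as a surrogate for KNDy neuron activity. A reader of the by-visit hormone table would take Weeks 4, 8 and 12 as a time course on one footing. If levels differ between predose and 3 hours postdose, part of any movement between Week 4 and Week 8 would come from sampling time. The Week 4 predose value, the only one comparable with the other visits, would be missing from the table.

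**Working it through.** The plan states no figure on this point to reproduce. The check applies the rule of SAP 7.10.6.1 to the sampling schedule.

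**Inputs**
- Targets and windows (SAP 7.10.6.1): Week 4, D29 (D22 to D36); Week 8, D57 (D50 to D64); Week 12, D85 (D78 to D92).
- Visit tolerance of ±3 days (protocol 6.3), so Visit 3 falls on D26 to D32, inside the Week 4 window.
- Study day is a difference of dates, so both samples from one day have the same study day.

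**Rule:** among values in the window, keep the smallest |study day − target day|; on a tie, keep the later value.

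**As scheduled.** For Visit 3 on D26, D27, D28, D29, D30, D31 and D32, the distance to D29 is 3, 2, 1, 0, 1, 2 and 3 days. It is the same for the predose and the 3-hour sample each time. That is a tie in 7 of 7 cases, and the later value is the 3-hour one in all 7.

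**With the shift provision** (other visits on target):

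| 3-hour sample taken | Week 4 keeps | Week 8 keeps | Week 12 keeps |
|---|---|---|---|
| Visit 3 day (D26 to D32) | 3-hour | predose | predose |
| Visit 4, D57 | predose | 3-hour | predose |
| Visit 5, D85 | predose | predose | 3-hour |
| Unscheduled D33, Visit 3 on D29 | predose | predose | predose |

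The last row depends on distance: |33 − 29| = 4 against 0, so the predose sample is nearer and is kept. An unscheduled day nearer to target would reverse this. With Visit 3 on D26 (distance 3) and the 3-hour sample on D30 (distance 1), the 3-hour value would be kept for Week 4.

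**Effect on the summary.** Let δ be the mean 3-hour value minus the mean predose value at a visit.
- Like-for-like Week 4 change = mean predose at Week 4 − mean predose at baseline.
- Change under the literal rule, all subjects sampled as scheduled = the like-for-like change + δ.
- If the true predose level is the same at Weeks 4 and 8, the table shows a Week 4 to Week 8 movement of −δ.
- If a fraction p has the 3-hour sample moved to the Week 8 or Week 12 visit day, that visit's mean moves by p × δ (δ taken in those subjects).

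The documents give neither δ nor p, so these expressions cannot be turned into numbers.

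**The case against.** The best case against is that the rule compares assessment days and was probably meant for samples on different days. The SAP's own schedule footnote treats the two Week 4 samples as distinct, and the TLF specifications or the separate PK/PD plan, neither of which is available here, may split them. That is possible. But the SAP contains no such exemption. If the tie rule does not reach same-day samples, the SAP has no rule for choosing between them, and the same clarification is needed. Treating the hormones as safety data does not help, because SAP 7.10.6.2 has the same tie rule.

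It is also fair that the consequences are limited. Hormones receive descriptive statistics only, with no test and no place in the step-down procedure. Sampling dates and times are recorded, so nothing is lost for good. This stands.

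Three stronger readings are tempting and are not supported:
- **That the table would show a false loss of LH suppression from peak to trough.** The documents say 3 hours postdose. They do not say when suppression is greatest, nor how far any of the four hormones differs between the two times.
- **That the artefact is larger in the QD arms.** Protocol 5.2 doubts that a QD morning dose suppresses KNDy activity at night, which makes a regimen difference plausible. It gives no hormone figure from which to infer one at these sampling times.
- **That the Week 12 endpoint is corrupted.** As scheduled, baseline and Week 12 are both predose. Contamination needs the 3-hour sample to be moved to the Week 12 visit day. Protocol 8.2 allows this for PK samples, while protocol 5.5.3 confines supervised morning dosing at the site to Day 1, Week 4 and Week 8. Those two sections should be reconciled.

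The SAP's ECG section does refer to visit and time point, but ECGs have one session per visit. That wording may be template text and does not show a deliberate omission for hormones.

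**Conclusion.** The point holds on the text of the SAP. For every subject sampled as scheduled, the literal rule reports the 3-hour postdose sample as the Week 4 hormone result and compares it with a predose baseline. Weeks 8 and 12 stay predose unless the 3-hour sample is moved to one of those visit days. The mix can therefore also differ between subjects within a visit.

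The selection itself rests on no numerical assumption. It assumes only that the SAP is followed as written and that the later of two same-day samples means later by clock time. The numerical effect is unknown and is zero if hormone levels do not differ between the two times. Severity is minor to moderate: the Week 4 summary and the visit-to-visit pattern are at risk, while the named Week 12 endpoint is unaffected as scheduled and the co-primary analyses are unaffected throughout.

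**What to change.** - In SAP 7.10.6.1, state that for PD samples the window and tie rule apply within nominal time point, predose and 3 hours postdose separately. A shifted 3-hour sample keeps its 3-hour label whichever day it is taken.
- State that by-visit changes at Weeks 4, 8 and 12 use predose values, because the baseline is predose. Separating the time points is the essential step; this one makes the changes like for like.
- Summarize the 3-hour sample as its own time point.
- Extend the hormone sentence in SAP 7.4.2 so that summaries are by visit and time point.

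The cost is a few SAP sentences and matching table shells, settled before database hard lock and unblinding. No extra samples or data are needed, since protocol 8.3 already requires the exact date and time of each draw.

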7.10.6.2 Safety Visit Windows

For the weeks on treatment (weeks prior to the follow-up period), the last day is always the day after the last day of exposure to treatment.

All safety assessments, including those from unscheduled visits and regardless of visit label, will be allocated to analysis visits based on the table below:

CRF visit	Target day	Actual assessment day	Analysis visit
Visit 1	D-35	D-35 to D-1	Screening
Visit 2	D1	D1	Baseline
Visit 2A	D15	After first dose to D22	Week 2
Visit 3	D29	D23 to D36	Week 4
Visit 3A	D43	D37 to D50	Week 6
Visit 4	D57	D51 to D64	Week 8
Visit 4A	D71	D65 to D78	Week 10
Visit 5	D85	D79 to Day 92	Week 12
End of treatment	Last dosing day + 1 day	Closest observation to the date	EOT
Visit 6	D106	Last assessment after date of completion or termination of treatment period	Week 15 Follow-Up

The value which assessment day is the closest to the defined target day within these windows is used. If two values are equally close, the latter is used in the analysis.

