9.10 Electrocardiograms

Twelve-lead digital ECGs will be obtained at each study visit (excluding Visits 2A, 3A, and 4A) after 10 minutes in a supine position. Whenever vital signs, 12-lead ECGs, and blood draws are scheduled for the same nominal time, the assessments should occur in the following order: 12-lead ECG, vital signs, and blood draws.

Skin preparation should be thorough and electrodes should be placed according to standard 12-lead ECG placement.

Electrocardiograms will be digitally recorded and printed on paper. All 12-lead ECGs will be captured in triplicate (ie, 3 separate 12-lead ECGs at least 1 to 2 minutes apart within a 5-minute window). The printed paper ECGs will be used for “real time” bedside ECG assessment by the Investigator (or designee) who will be responsible for the overall interpretation and determination of the clinical significance of any potential ECG findings. Digital ECGs will be submitted to the ECG core laboratory, which will perform the digital ECG analysis and interpretation in this study using standard methodology. If the central reader identifies an abnormality, per the study alert criteria, the Investigator will be notified who will review the ECG and report any adverse events as necessary.

The following variables will be reported: HR, RR, PR, QRS, QT, QTcB, and QTcF intervals. The Investigator may add additional 12-lead ECG safety assessments if there are any abnormal findings or if the Investigator considers it is required for any other safety reason. Refer to Appendix E for normal ranges for ECG parameters.

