7.5.4 Electrocardiograms (ECGs)

The baseline visit is the last measurement taken prior to initial study drug administration.

ECG variables will be summarized using (n), mean, standard deviation, minimum, median, maximum, 10%, 90%, and lower and upper quartiles for each treatment group at each treatment visit, including changes from baseline.

Number and percent of subjects with normal, not clinically significant abnormal, and clinically significant abnormal results as assessed by investigator for the 12 lead ECG will be tabulated by treatment group at each treatment visit. Local readings and central readings will be summarized separately.

The QT intervals (QT, QTcB, and QTcF) will be summarized using frequency tables for each treatment visit (excluding Visits 2A, 3A, and 4A) and time point for values of clinical importance using the range criteria below.

QT Interval Criteria (msec)	Description
≤450	Normal
>450	Borderline
>480	Prolonged
>500	Clinically significant

The QT intervals will also be summarized by the frequencies of subjects with a change from baseline of clinical importance using the criteria identified below. These summaries will be provided for each treatment visit and time point.

Parameter	Change from Baseline Criteria
QT Interval (msec)	<0
	≥0
	>30
	>60

Number and percent of subjects whose 12 lead ECG reading changed from normal at baseline to abnormal will be tabulated by treatment group for each visit.

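### An unscheduled QTc peak can go uncounted in the SAP's QT category tables, which take one ECG per visit window, omit Weeks 2, 6 and 10 from the absolute table and have no worst-value row

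*SAP*

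**What the plan says.** **Collection.** Protocol 9.10 schedules ECGs as follows: "Twelve-lead digital ECGs will be obtained at each study visit (excluding Visits 2A, 3A, and 4A"). Each is a set of three: "All 12-lead ECGs will be captured in triplicate", all inside five minutes. Extra ECGs are allowed: "The Investigator may add additional 12-lead ECG safety assessments if there are any abnormal findings", or on other safety grounds.

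**Allocation.** SAP 7.5 applies the visit windows of 7.10.6 to by-visit safety analyses and, apart from adverse events and follow-up data, stops at one day after the last dose. SAP 7.10.6.2 windows all safety assessments by study day, unscheduled ones included and whatever their visit label. Within a window the value nearest the target day is used. For ties: "If two values are equally close, the latter is used in the analysis".

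**Tabulation.** SAP 7.5.4 has two QT tables covering QT, QTcB and QTcF.
- The absolute categories (up to 450, >450, >480, >500 ms) are "summarized using frequency tables for each treatment visit (excluding Visits 2A, 3A, and 4A) and time point".
- The change categories (<0, at least 0, >30, >60 ms) carry no such exclusion: "These summaries will be provided for each treatment visit and time point".

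The ECG baseline is defined in one sentence: "The baseline visit is the last measurement taken prior to initial study drug administration". Neither table has a row for the worst on-treatment value. The liver table in SAP 7.5.2.1 does work that way, taking each subject's highest on-treatment result.

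**The concern.** A QT category table exists to show how many subjects ever crossed a threshold. An ECG that the investigator adds because of an abnormal finding is the one most likely to show a crossing. The windowing rules choose an ECG by its date and ignore its value, and the absolute table then omits three of the six on-treatment windows.

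The scheduled ECGs are an incomplete substitute. Footnote a of the schedule of procedures has all assessments done before the dose, apart from the Week 4 PK and PD blood samples. An added ECG may therefore be the only one taken soon after a dose or during symptoms. At stake is a reported safety result across seven dose groups: a >480 or >500 ms value could be in the database while the table shows none.

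A second, smaller gap is that the SAP does not say how three tracings are reduced to one analysis value.

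**Working it through.** The plan states no figure for QTc (no SD, expected rate or precision), so there is none to reproduce. The check is a reading of the rules, a count of days and one illustrative calculation.

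**1. Days whose ECGs are left out of the absolute table** (SAP 7.10.6.2)

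| Window | Days | Count |
|---|---|---|
| Week 2 (Visit 2A) | D2-D22, plus D1 after the dose | 21 |
| Week 6 (Visit 3A) | D37-D50 | 14 |
| Week 10 (Visit 4A) | D65-D78 | 14 |
| Total | | 49 |

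D2 to D85 is 84 days, and 49/84 = 58%. The other 35 days are D23-D36 (14), D51-D64 (14) and D79-D85 (7).

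**2. Effect on scheduled ECGs.** Visits may move by 3 days. Visit 3 then falls on D26-D32, Visit 4 on D54-D60 and Visit 5 on D82-D88. All lie inside the Week 4, 8 and 12 windows, and no ECG is scheduled at 2A, 3A or 4A. The exclusion removes no scheduled ECG from these visits.

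**3. Week 4, 8 and 12 windows.** One value per window survives. As an example, take a scheduled ECG on D30 and an unscheduled one on D34. Their distances from the D29 target are 1 and 5 days, so the D34 ECG is dropped whatever its QTc. If the scheduled ECG is on D29, no ECG from another day in that window can be selected. This rule feeds the change table as well as the absolute table.

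**4. The end-of-treatment row.** It takes the ECG nearest to one day after the last dose. It can recover a peak in a subject who stopped treatment close to that ECG. For a subject who completes 12 weeks it points to the Week 12 period, so it does not recover a peak in the Week 2, 6 or 10 window.

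**5. Triplicates.** Three tracings in one five-minute set share an assessment day. Read literally, the tie rule and the baseline sentence would both select the last tracing. To show what that would cost, let b be the between-occasion SD, s the within-occasion SD and k the number of tracings averaged:

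SD of change = √(2(b² + s²/k))

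The documents give neither SD. Assume b = 8 ms and s = 5 to 10 ms.
- One tracing (k = 1): √(2(64 + 25)) = 13.3 ms to √(2(64 + 100)) = 18.1 ms.
- Mean of three (k = 3): √(2(64 + 8.33)) = 12.0 ms to √(2(64 + 33.3)) = 14.0 ms.

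With no drug effect and normal errors, the chance of a change above 30 ms is 1.2% to 4.9% per subject-visit for one tracing, against 0.6% to 1.6% for the mean. Over b = 5 to 10 ms and s = 4 to 10 ms, the ratio of the two SDs runs from 1.05 to 1.46. Its upper limit, at b = 0, is √3 = 1.73.

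**The case against.** **Leaving out 2A, 3A and 4A matches the ECG schedule.** This stands for scheduled data (step 2). The exclusion is also written only for the absolute table, so a reader should not carry it over to the >30 and >60 ms changes. It does not answer for unscheduled ECGs, which the SAP expressly assigns to those windows.

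**A serious QTc peak would be seen elsewhere.** The core laboratory alerts the investigator (Protocol 9.10), clinically significant ECG findings are reported as adverse events (Protocol 9.1), and subject listings are planned (Protocol 10). This softens the consequence, since the value is not lost to the report. It does not correct the count in the table that is meant to show it.

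**SAP 7.10.5 includes all values.** That sentence concerns outliers. It does not override the rule of one value per window.

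**The triplicates may be averaged upstream.** A reader might infer that the SAP keeps only the third tracing and discards two thirds of the ECG data. The documents do not support that. The tie rule is generic windowing text, keyed to assessment day and repeated for efficacy assessments in 7.10.6.1. The baseline sentence is the same one used for laboratory tests and vital signs. Averaging by the core laboratory is neither stated nor ruled out. What stands is that the rule is unspecified. Core-laboratory averaging would also leave open the local readings, which SAP 7.5.4 summarizes separately.

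**Extra measurement noise would be shared by all arms.** That is correct: it would cost precision and would not favour one arm. It is also unrelated to the exclusion of 2A, 3A and 4A.

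**Conclusion.** The concern holds for unscheduled ECGs. On 49 of the 84 days from D2 to D85 (58%), an unscheduled ECG goes to a window that the absolute QT table omits. On the other days it is dropped if another ECG is nearer the target day. A true peak above 450, 480 or 500 ms can therefore be missing from that table unless it is the end-of-treatment value. The change table has no written exclusion but uses the same one-value rule, and neither table has a worst-value row.

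The 58% is a share of calendar days. It is not a share of unscheduled ECGs or of peaks, because the documents give no rate for either. The conclusion assumes the windows are programmed as written.

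The handling of triplicates is a point to clarify and not a demonstrated error. The noise figures rest on assumed SDs and only illustrate the direction. No efficacy conclusion is affected.

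**What to change.** **Main change, SAP 7.5.4.** Add a worst on-treatment row to the absolute and the change tables for QT, QTcB and QTcF. Build it from all post-dose on-treatment ECGs, including unscheduled ones in the Week 2, 6 and 10 windows, and state that the window selection in 7.10.6.2 does not apply to this row. The by-visit rows can stay as they are.

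**Clarification, SAP 7.5.4 and 7.10.6.2.** State that each ECG value, baseline included, is the mean of the available replicates at that time, and apply the nearest-day and tie rules to those means. If the core laboratory already supplies means, say so for the central readings and state what is done for the local ones.

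**Cost.** SAP wording and minor extra programming before database lock, with no new data.
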